In 2017, the World Health Organization issued guidelines for integrated care for older people (ICOPE) for older people in communities. The guide clearly points out that it is necessary to organize all the resources that can be mobilized in the community to provide unified and integrated care services for older people; The goal of the service focuses on improving the functional capacity of older people, dealing with cognitive decline, urinary incontinence, falls, malnutrition, caregiver burden, and other problems unique to older adults; It is recommended that all countries and regions refer to this guide to explore their own specific and operable model processes. At present, the health services for older people in the community in China are still mainly outpatient services in hospitals at all levels, lacking unified health management and the concept and practice of integrated care. The implementation of integrated care in the community is conducive to effectively promoting the integration of medical care and social care, which is consistent with the purpose of the state to provide elderly care services in the community.

ICOPE model is aimed at providing people-oriented, value-based health and care services for older people throughout the life course. It needs to be comprehensively considered, designed, and implemented from the top-level design, policy guidance, payment mechanism, service capacity-building, and the management of measurable results.

In the United Nations Decade of Healthy Ageing (2021-2030), integrated care for older people is set as one of the core actions for World Health Organization. The first batch of global pilot projects of ICOPE are implemented in seven countries. The Chinese pilot was carried out by Pinetree Care Group and the Department of Geriatrics, Peking Union Medical College Hospital, in conjunction with a number of general hospitals and hundreds of community health and care service centers, with more than 2000 older people. The pilot was conducted in Chaoyang District, Beijing.

2. Research purpose

The goal of this pilot study is to evaluate the feasibility of implementing World Health Organization's ICOPE (integrated care for older people) approach in China. The main questions it aims to answer are:

- 1) Whether it is feasible to implement the ICOPE approach in China;
- 2) Whether the integrated care approach would make any difference in health outcomes and resource utilization.

For the first question, predefined parameters such as sample size, capacity building, acceptance by community-dwelling older people (participants) and care providers were examined.

3. Research methods

Prospective randomized controlled study. A total of 2000 community-dwelling older persons aged 60 and above at-risk of functional loss in Chaoyang District of Beijing are recruited and randomly assigned to the intervention group (n=500) and control group (n=1500).

3.1. Primary Outcome Measure:

Feasibility of implementing the ICOPE program in China:

- 1) Sample size (to successfully recruit over 2,000 participants, 500 of whom were to be categorized in the intervention group)
- 2) Capacity building (at least 200 primary care providers to be fully trained and deployed in the pilot program)
- 3) Acceptance (reach more than 90% satisfaction with the pilot by both participants and providers).

3.2. Secondary Outcome Measures:

Independence - measured by the activities of daily living (ADL) 14-questionnaire scale, to assess the participant's physical function.

Cognition - measured by mini-mental status examination (MMSE) to assess the cognitive health of the participants.

Vitality - nutrition measured by mini-nutritional assessment- short form (MNA-SF) to assess the risk of malnutrition.

Mobility - measured by short physical performance battery (SPPB) to assess the risk of declining mobility.

Psychological health - measured by geriatric depression scale-five items (GDS-5) using a short set of questions to assess possible depressive symptoms.

4. Statistical methods and sample size

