4.1. Sample size calculation

At present, there is no specific local data to support the calculation of sample size.

Using all-cause death and falls as the endpoint events, based on previous literature and pre-experimental data, the percentage of decline in intrinsic ability in the community elderly population as the dependent variable ranged from 43.0% to 77.4%, and the incidence of all-cause death, falls and functional decline in the group with decline in intrinsic ability at 3-year follow-up was 16.4%, 55.3% and 64.8%, respectively, using PASS software, setting a two-sided $\alpha=0.05$ with 90% certainty, based on the above data, it was calculated that at least 58 people with all-cause death as the endpoint event of decline in intrinsic ability, 72 people with falls as the endpoint event, and 126 people with decline in function as the endpoint event were required, considering that the population included in this study was elderly, and based on previous studies, the proportion of decline in intrinsic ability was estimated to be 70%, and considering a 5% loss of follow-up rate, at least 190 elderly people. Therefore, a total of 380 individuals were included in the intervention and control groups (intervention community and control community).

This project plans to investigate and follow up with at least 2000 older people and intervene in more than 500 cases. Combined with the sample size calculation above, this project should meet the needs of sample size.

4.2. Statistical methods:

STATA will be used to establish the database and conduct statistical analysis.

The baseline data were collected, and the corresponding statistical methods were selected according to the data type to compare the basic clinical information of patients: if the data conformed to the normal distribution, it was expressed as the mean \pm standard deviation ($\pm s$),

and the independent sample t test was used for the comparison between the two groups; If the data does not conform to the normal distribution, it is expressed as the median (25th percentile, 75th percentile), and the Mann Whitney U test is used for the comparison between the two groups.

The intervention group and the control group were propensity matched, and the incidence of adverse health outcomes (all-cause death, falls, functional decline) and changes in quality of life (self-control, comparison between the two groups) were compared between the two groups.

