5.2 Randomization

A random number table (1-2000 random order) was established and managed by a dedicated person (who was only responsible for informing the number). The older person who met the enrollment conditions received random numbers according to the order of the random number table. The random number divided by 3 is an integer, and the remaining 1 is the control group, and the remaining 2 is the intervention group.

6. Research process

6.1 Data acquisition and observation indicators:

- (1) The elderly who met the inclusion criteria were included, and their demographic characteristics (gender, age, education, height, weight, BMI, smoking and drinking history) were recorded
- (2) Assessment of intrinsic ability: according to the screening tool for integrated care for older people (ICOPE) and the people-centered assessment guide issued by WHO, there are five dimensions in total, with 1 point for each dimension. Impairment in any dimension is defined as a decline in intrinsic ability. See Case Report Form (CRF) for the rating scale of each dimension.

Cognitive dimension: Mini Mental State Examination (MMSE), with a total score of 30 points. According to the education level of the research object, whether there is cognitive dysfunction is defined. Illiteracy ≤ 17 points, primary school level ≤ 20 points, secondary school level (including technical secondary school) ≤ 22 points, university level (including junior college) ≤ 23 points. Vitality: the mini nutritional assessment short form (MNA-SF) has

a total score of 14 points. A score of 12-14 defines normal nutritional status, 8-11 indicates malnutrition risk, and 0-7 indicates malnutrition.

Psychology: the total score of the geriatric depression scale 15 item (GDS-15) is 15 points, and a score of ≥ 5 points is defined as depression (Appendix 3). Or the Zung Depression Scale (SDS) was used for evaluation. Standard score = total score \times 1.25, take an integer, and a standard score > 50 points is considered as depression.

Exercise: the short physical performance battery test (SPPB), including the evaluation of sitting up test, gait speed test and balance test, has a full score of 4 points for each part, a total score of 12 points, and a score of ≤ 9 points is considered as physical function decline.

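### The primary recruitment criterion asks for over 2,000 participants, but the plan as written delivers exactly 2,000: the target needs one wording, and the 500 needs reconciling with the allocation rule

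*Combined protocol and SAP*

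**What the plan says.** The combined protocol and SAP gives the recruitment target in five places.

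- Background, before section 2: the pilot is described as run "with more than 2000 older people".
- Section 3, design sentence: "A total of 2000 community-dwelling older persons aged 60 and above at-risk of functional loss" are to be recruited and "randomly assigned to the intervention group (n=500) and control group (n=1500").
- Section 3.1, first primary feasibility criterion: "to successfully recruit over 2,000 participants, 500 of whom were to be categorized in the intervention group".
- Section 4.1, closing paragraph: "This project plans to investigate and follow up with at least 2000 older people and intervene in more than 500 cases".
- Section 5.2: "A random number table (1-2000 random order) was established", and eligible people take numbers from it in order. Allocation is by the remainder after dividing the number by 3.

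The plan does not say that recruitment stops at 2,000, does not provide for extending the table, and does not define who counts as recruited. Section 4.2 gives no test, interval or decision rule for feasibility, so comparing the count with the threshold is the whole analysis of this criterion.

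**The concern.** Feasibility is the primary outcome, and section 3.1 lists recruitment first among its three criteria. A pass mark of this kind has to be a single number fixed in advance. Here the pass mark in section 3.1 lies just above the total planned in section 3 and just above the last number in the table in section 5.2, while section 4.1 uses a slightly lower one. If recruitment ends where the plan says it should, the reported verdict depends on which section the author cites.

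The intervention-arm part of the criterion has a similar problem. It is 500 in sections 3 and 3.1 and more than 500 in section 4.1, and the allocation rule in section 5.2 is not aimed at either figure.

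**Working it through.** **Inputs.** Planned arms of 500 and 1500 (section 3). Thresholds of over 2,000 (section 3.1) and at least 2000 (section 4.1). Table numbers 1 to 2000 and the divide-by-3 rule (section 5.2).

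**Step 1: the plan's own total.** 500 + 1500 = 2000. This reproduces the figure in section 3 and equals the number of entries in the table.

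**Step 2: that total against each threshold.** The smallest whole number over 2,000 is 2,001.

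| Number recruited and randomised | Over 2,000 (3.1) | At least 2,000 (4.1) |
|---|---|---|
| 1,999 | fail | fail |
| 2,000 | fail, short by 1 | pass |
| 2,001 | pass | pass |

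The two wordings disagree in one row only, the row for the planned total and the filled table. The 2,001 row needs one more number than the table holds.

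**Step 3: the intervention arm as worded.** With 500 as planned, the figure in sections 3 and 3.1 is met exactly. More than 500 (section 4.1) is not met, again by one.

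**Step 4: the intervention arm that section 5.2 produces.** On the natural reading, exact division and remainder 1 go to control, and remainder 2 goes to intervention. Counting 1 to 2000:

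- remainder 0: 666 numbers
- remainder 1: 667 numbers
- remainder 2: 667 numbers

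Control = 666 + 667 = 1,333. Intervention = 667. Total = 1,333 + 667 = 2,000, so every number is assigned.

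The planned intervention share is 500 / 2000 = 25.0%. The share under the rule is 667 / 2000 = 33.35%. The arms differ from the plan by 667 − 500 = 167 more in intervention and 1,500 − 1,333 = 167 fewer in control.

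**Step 5: consequence for the 500.** With one number in three going to intervention, 500 is reached after about 3 × 500 = 1,500 randomisations. A target of at least 500 would therefore be passed well before the total target and would hide the mismatch with section 3.

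**The case against.** The strongest reply is that this is a one-person ambiguity around a round number. The background and section 4.1 both treat 2,000 as a floor, nothing caps recruitment there, and a table can be lengthened. The criterion also speaks of recruiting, not randomising. At 1,999 or fewer both thresholds fail and at 2,001 or more both pass, so a feasibility conclusion would rarely turn on the difference.

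Most of this stands, and it limits the point. Two things remain. The single value at which the verdicts differ is the one the design sentence and the table both lead to. And section 3 has the same 2,000 people recruited and randomised, so treating the two counts as one follows the plan's own wording; if another count was meant, it is not defined.

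Two stronger readings are tempting. A reader might infer that the criterion is bound to fail, even with full recruitment. The documents do not support that, because section 4.1 and the background allow for more than 2,000 and no stopping rule is given. A reader might also infer from the awkward sentence in section 5.2 that numbers divisible by 3 go to no arm, leaving 667 + 667 = 1,334 assigned. The sentence more naturally places exact division and remainder 1 together in control, and section 3 assigns everyone recruited to one of two arms. Even on that reading, the unassigned people would still have been recruited.

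**Conclusion.** The point holds as an inconsistency in a primary decision threshold. Following sections 3 and 5.2 exactly gives 2,000 randomised, which misses the section 3.1 wording by one and meets the section 4.1 wording. This assumes that recruited means enrolled and randomised, and that the table is used as written without extension. It does not show that the criterion is unattainable, and it does not bias the comparison between groups.

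The larger numerical conflict inside the same criterion is the intervention arm: 500 of 2,000 as planned against 667 of 2,000 under the allocation rule, a difference of 167 people in each arm. That figure assumes the natural reading of section 5.2 and a fully used table.

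**What to change.** 1. Use one threshold in sections 3, 3.1 and 4.1: at least 2,000 participants enrolled and randomised. The existing table of 1 to 2000 can deliver this, so it need not be longer. The wording also settles who is counted.
2. Record which wording governed the feasibility verdict, and when it was fixed relative to the recruitment count.
3. State the intervention-arm target once, choosing between 500 and more than 500, and reconcile it with section 5.2. If 500 and 1,500 are intended, the rule has to give one in four; for example, dividing by 4 and sending one remainder to intervention gives 2000 / 4 = 500 and 2000 − 500 = 1,500. If the divide-by-3 rule was the one used, restate the planned arms as 667 and 1,333. Do not simply relax 500 to at least 500, because that leaves the conflict in place unseen.

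Items 1 and 2 cost a wording change and a short note. Item 3 costs a correction to either the planned arm sizes or the description of the rule. If allocation has already taken place, the text should describe the procedure actually used. None of this adds participants.

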4.1. Sample size calculation

At present, there is no specific local data to support the calculation of sample size.

Using all-cause death and falls as the endpoint events, based on previous literature and pre-experimental data, the percentage of decline in intrinsic ability in the community elderly population as the dependent variable ranged from 43.0% to 77.4%, and the incidence of all-cause death, falls and functional decline in the group with decline in intrinsic ability at 3-year follow-up was 16.4%, 55.3% and 64.8%, respectively, using PASS software, setting a two-sided $\alpha=0.05$ with 90% certainty, based on the above data, it was calculated that at least 58 people with all-cause death as the endpoint event of decline in intrinsic ability, 72 people with falls as the endpoint event, and 126 people with decline in function as the endpoint event were required, considering that the population included in this study was elderly, and based on previous studies, the proportion of decline in intrinsic ability was estimated to be 70%, and considering a 5% loss of follow-up rate, at least 190 elderly people. Therefore, a total of 380 individuals were included in the intervention and control groups (intervention community and control community).

This project plans to investigate and follow up with at least 2000 older people and intervene in more than 500 cases. Combined with the sample size calculation above, this project should meet the needs of sample size.

4.2. Statistical methods:

STATA will be used to establish the database and conduct statistical analysis.

The baseline data were collected, and the corresponding statistical methods were selected according to the data type to compare the basic clinical information of patients: if the data conformed to the normal distribution, it was expressed as the mean \pm standard deviation ($\pm s$),

and the independent sample t test was used for the comparison between the two groups; If the data does not conform to the normal distribution, it is expressed as the median (25th percentile, 75th percentile), and the Mann Whitney U test is used for the comparison between the two groups.

The intervention group and the control group were propensity matched, and the incidence of adverse health outcomes (all-cause death, falls, functional decline) and changes in quality of life (self-control, comparison between the two groups) were compared between the two groups.

$P < 0.05$ indicates that the difference is statistically significant.

5. Patient enrollment and exclusion criteria

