6.3 Follow-up

Follow-up time: 3 Months, 6 Months from baseline

Follow up will be carried out through telephone, family doctor visit, medical record system review, and the ADL score, frailty scale score, and adverse health outcomes (falls, recurrent falls, severe falls, all-cause death) were recorded.

Record the time of the first fall, which can be specific to month, such as December 2020. If the person or family member can't remember clearly, they can provide the time range, such as January to June 2021.

The time and cause of all-cause death (including the direct and chronic causes of death, such as severe pneumonia and dementia) were recorded.

The intervention group with decreased intrinsic capacity will go through a comprehensive assessment. Intervention group will be re-assessed at 3 months and 6 months after baseline, while the control group will be assessed at baseline and 6 months.

7. Benefits and risks of research

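### Section 4.1 does not support the 6-month between-arm comparison of death, falls and functional decline: its inputs are 3-year incidences and it states no comparator rate or effect

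*Combined protocol and SAP*

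**What the plan says.** Section 4.1 opens by conceding that "At present, there is no specific local data to support the calculation of sample size". It then takes all-cause death, falls and functional decline as endpoint events, with incidences that "in the group with decline in intrinsic ability at 3-year follow-up was 16.4%, 55.3% and 64.8" percent. At a two-sided alpha of 0.05 and "with 90% certainty, based on the above data, it was calculated that at least 58 people" are needed for death, followed by 72 for falls and 126 for functional decline. Because "the proportion of decline in intrinsic ability was estimated to be 70" percent and 5% loss is expected, the number becomes 190. The section continues: "Therefore, a total of 380 individuals were included in the intervention and control groups". The project plans to "follow up with at least 2000 older people and intervene in more than 500 cases", and 4.1 ends: "Combined with the sample size calculation above, this project should meet the needs of sample size".

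Section 4.2 compares the incidence of the same three events between the two groups after propensity matching. Section 6.3 gives "Follow-up time: 3 Months, 6 Months from baseline". Section 3 plans 500 intervention and 1,500 control participants. Section 5.1 admits only people whose decline has been confirmed.

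**The concern.** A two-group power statement needs an event risk over the actual follow-up and either a second risk or an effect. Section 4.1 has neither. Its event rates cover 3 years, six times the planned follow-up, and there is one rate per endpoint. Its other percentages (43.0% to 77.4%, and 70%) are prevalences of intrinsic-capacity decline, not event rates in a comparison group. The wording reads more like a comparison of people with and without decline than of intervention with control, although that is an inference.

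What is at stake is the second study question in section 2 (health outcomes) and the comparisons in 4.2. A reader of 4.1 may take those comparisons to have 90% power, and may then read a null result on death or falls as good evidence of no effect.

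**Working it through.** **1. The plan's own figures.** The last step reproduces: 126 / 0.70 / 0.95 = 189.5, rounded up to 190; 2 × 190 = 380.

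The numbers 58, 72 and 126 cannot be rebuilt, because an input is missing; nor can they be called wrong. Read as people per arm at 90% power, they imply a lower comparator rate of 0.1% (death), 29.0% (falls) and 44.6% (functional decline). These are risk ratios of about 0.01, 0.52 and 0.69, so no common effect lies behind them.

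**2. The 0.70 factor.** Everyone enrolled has confirmed decline (5.1), so an allowance for people without decline does not apply. Without it, 126 / 0.95 = 132.6, so 133. This is an inconsistency only: it raises the number and costs no power.

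**3. From 3 years to 6 months (assumption).** With a constant hazard, the 6-month risk is 1 − (1 − p)^(1/6):

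- death: 1 − 0.836^(1/6) = 0.0294
- falls: 1 − 0.447^(1/6) = 0.1256
- functional decline: 1 − 0.352^(1/6) = 0.1597

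As a range I use p/6 to p/3: 0.0273–0.0547, 0.0922–0.1843 and 0.1080–0.2160. Constant hazard is rough for functional decline, which can reverse. Among 190 people, the central values give about 6 deaths, 24 people with falls and 30 with functional decline.

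**4. Power.** Two-proportion pooled z-test, two-sided 0.05. With control risk c, intervention risk i = RR × c and pooled risk m:

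power = Φ{[(c − i) − 1.96 √(m(1 − m)(1/n_c + 1/n_i))] / √(c(1 − c)/n_c + i(1 − i)/n_i)}, plus the opposite tail, which is small.

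Example: falls, 500 intervention and 1,500 control, RR 0.6. c = 0.1256, i = 0.0754, m = 0.1130. The numerator is 0.0502 − 1.96 × 0.01635 = 0.0182 and the denominator is 0.01458. Their ratio is 1.25, so power is 89%.

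Power in %, for death / falls / functional decline. The range over p/6 to p/3 is in brackets.

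| Intervention:control | 40% reduction | 30% reduction |
|---|---|---|
| 190:190 (4.1) | 12 (11–18) / 37 (28–53) / 46 (32–61) | 9 / 22 / 28 |
| 500:1500 (section 3) | 27 (25–50) / 89 (76–98) / 96 (83–99) | 16 / 63 / 76 |
| 667:1333 (5.2, remainder 0 read as control) | 34 (31–59) / 94 (84–99) / 98 (90–100) | 20 / 72 / 83 |
| 667:667 (5.2, remainder 0 left out) | 29 (28–50) / 86 (73–97) / 94 (80–99) | 18 / 61 / 72 |
| 500:500 (if matched 1:1, a ratio the plan does not state) | 23 (22–39) / 75 (61–91) / 86 (68–95) | 15 / 49 / 60 |

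The rows for 5.2 follow from dividing 1 to 2000 by 3: 666 numbers leave 0, 667 leave 1 and 667 leave 2; 666 + 667 = 1,333.

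With the plan's 5% loss, 475:1425 gives 26 / 88 / 95 for a 40% reduction. An exact binomial check for death at 40%, in row order, gives 10, 28, 34, 29 and 23; its highest value over the range is 60%, at 667:1333.

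**5. Detectable effect at 90% power (constant hazard).** At 190:190 the risk ratio must be about 0.28 for falls and 0.36 for functional decline. For death, even zero intervention deaths gives only about 81% (exact). At 500:1500 the values are about 0.23 (death), 0.60 (falls) and 0.64 (functional decline).

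**The case against.** The strongest reply is that nobody plans a trial of 380. That figure is a minimum, and the plan is for at least 2,000 with more than 500 intervened. At 500:1500 and a 40% reduction, falls and functional decline reach 89% and 96%. This stands: the 380 results describe the stated requirement, not the study, and a study above its minimum would do better. But at a 30% reduction the same two figures are 63% and 76%, and death is short throughout. Enrolling more people also does not supply the missing time horizon or effect, and the closing assurance in 4.1 rests explicitly on the calculation before it.

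It is also fair that the primary outcome is feasibility, that death and falls are not among the secondary outcomes in 3.2 (which are scales), and that a pilot's secondary comparisons need not have 90% power. This limits the consequence. It does not justify stating an assurance that the calculation cannot give.

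Finally, the illustration rests on several assumptions: certainty read as power, the 6-month risks, the risk ratio and the group sizes. The mention in 4.1 of an intervention community and a control community could even mean allocation by community, which would make individual-level power too high; section 3 and 5.2 do not describe that. The two textual points, the time horizon and the missing effect, need none of these assumptions.

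**Conclusion.** The concern holds as an unsupported justification, not as an arithmetic slip. The 3-year inputs, the 6-month follow-up and the absence of any comparator rate or effect are all on the page. If certainty does not mean power, 4.1 contains no power statement at all and the comparison is still unsupported.

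The size depends on assumed 6-month risks and effects. For reductions of 30–40%, no event exceeds about 61% power at 380 people, and death does not exceed about 60% at any size tabulated. At about 2,000, falls and functional decline may be adequately powered for large effects. The feasibility outcome is not affected.

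**What to change.** In 4.1, withdraw the 90% statement, the 380 figure and the 0.70 factor as justification for the intervention comparison, and state that 2,000 is a feasibility target. Replace them with a short table of the detectable 6-month effect for each event over a stated range of 6-month risks, labelled as assumptions. Use the group sizes that will be analysed. This requires reconciling the 500:1500 of section 3 with the remainder rule in 5.2 (including which arm remainder 0 joins) and allowing for loss to follow-up and for the matching in 4.2. State plainly that the mortality comparison has low power.

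The background text before section 2 describes the pilot in the past tense. If the study is complete, report the same content as a limitation instead.

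The cost is a rewording of 4.1 and one short table, or one limitation paragraph. The stated power becomes less favourable, and no participants are added.

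### Section 4.2 spends P values on baseline differences between randomised arms, and no stated outcome analysis adjusts a secondary scale for its own baseline score

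*Combined protocol and SAP*

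**What the plan says.** - **Tests named.** Section 4.2 names two, both attached to baseline data. It says that "the corresponding statistical methods were selected according to the data type to compare the basic clinical information of patients". Normal data get a mean, a standard deviation and an independent-sample t test. For the rest, "If the data does not conform to the normal distribution, it is expressed as the median" with quartiles, and the test is Mann-Whitney. The significance threshold is 0.05.
- **Outcomes.** The same section says that the arms are propensity matched. It then says that the incidence of death, falls and functional decline, and changes in quality of life (within person and between arms), are compared. It names no outcome test, regression model, effect measure or confidence interval, and no matching covariates.
- **Secondary scales.** Section 3.2 lists ADL, MMSE, MNA-SF, SPPB and GDS-5. Section 4.2 mentions none of these scales by name.
- **Allocation.** Section 3 describes a randomised study of 500 intervention and 1500 control participants. Section 5.2 describes allocation of individuals: "The older person who met the enrollment conditions received random numbers according to the order of the random number table". A parenthesis in 4.1, however, speaks of an intervention community and a control community.
- **Timing.** Section 6.3 assesses the control arm at baseline and 6 months, and the intervention arm additionally at 3 months.

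**The concern.** Two things look wrong.

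First, if individuals were randomised as 5.2 describes, a baseline difference between arms arises by chance. A significance test on it answers no useful question, yet a small P value is easily read as failed randomisation.

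Second, a participant's own baseline score is usually a strong predictor of the later score on the same scale, and 6.3 has both arms assessed at baseline. No stated analysis uses that score as a covariate. The second research question in section 2 asks whether integrated care makes a difference to health outcomes. That calls for an estimated difference in scale points with an interval, as narrow as the collected data allow. With no analysis fixed for the five scales, the choice also stays open until the data are seen.

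**Working it through.** **The plan's own figure.** Section 4.1 reports, "setting a two-sided $\alpha=0.05$ with 90% certainty", that "126 people with decline in function as the endpoint event were required". Then 126 / 0.70 = 180, and 180 / 0.95 = 189.5, rounded up to 190 per group, or 380 in total. This reproduces the plan. The figure rests on event endpoints and gives neither a standard deviation nor a baseline to follow-up correlation for any scale, so it does not bear on precision for the secondary scales.

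**Baseline tests.** Section 6.1(1) lists 8 items: gender, age, education, height, weight, BMI, smoking and drinking. If all are tested at 0.05 and are independent, the chance of at least one P < 0.05 under valid randomisation is 1 − 0.95^8 = 0.34. BMI is derived from height and weight, so independence is only approximate. For the four plainly numeric items alone (age, height, weight, BMI) the same formula gives 1 − 0.95^4 = 0.19.

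**Precision.** Inputs from the plan: 500 and 1500 participants, two-sided 0.05, 90% power. Assumed: correlation r between baseline and month 6 from 0.3 to 0.8, equal SD at both times, and the same slope on baseline in both arms. Relative to comparing month-6 scores without adjustment:

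- baseline-adjusted model: variance factor 1 − r²
- change score: variance factor 2(1 − r)
- adjusted model relative to change score: (1 − r²) / [2(1 − r)] = (1 + r)/2

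The unadjusted detectable difference is (1.960 + 1.282) × √(1/500 + 1/1500) = 3.242 × 0.0516 = 0.167 SD. The other detectable differences are this value times the square root of the variance factor.

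| r (assumed) | Adjusted vs unadjusted, variance | Adjusted vs change, variance | Detectable, change (SD) | Detectable, adjusted (SD) |
|---|---|---|---|---|
| 0.3 | 0.91 | 0.65 | 0.198 | 0.160 |
| 0.5 | 0.75 | 0.75 | 0.167 | 0.145 |
| 0.7 | 0.51 | 0.85 | 0.130 | 0.120 |
| 0.8 | 0.36 | 0.90 | 0.106 | 0.100 |

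Below r = 0.5 a change score is less precise than ignoring baseline altogether.

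For a true difference of 0.15 SD, power is 82.8% unadjusted. At r = 0.3, 0.5, 0.7 and 0.8 it is 69.0%, 82.8%, 96.3% and 99.6% with a change score, and 86.1%, 91.8%, 98.2% and 99.8% with baseline adjustment.

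**Sensitivity to allocation.** Read literally, the remainder-2 rule in 5.2 sends 667 of the numbers 1 to 2000 to intervention. At 667:1333 the unadjusted detectable difference is 0.154 SD, and the variance factors do not change.

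**Matching.** The matching ratio is not given. If it were 1:1, up to 1000 controls would be dropped. The standard error would rise by √[(2/500) / (1/500 + 1/1500)] = 1.22 before any gain from matching.

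**The case against.** The strongest reply is that the plan is silent on the secondary scales, not explicitly unadjusted. That stands, and it limits the point in several ways.

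- A reader might infer that the normality rule carries over, so that each scale gets a Mann-Whitney test, and that the plan throws away the equivalent of 1/(1 − r²) = 1.6, 2.0 or 2.8 times the sample at r = 0.6, 0.7 or 0.8. The text does not support this. The rule is attached to baseline data only, and the one score-type comparison named is change, which does use baseline. Against change, the variance reduction at r = 0.6 to 0.8 is only 20% to 10%.
- A reader might count about 25 measurements in 6.1 and compute 1 − 0.95^25 = 0.72. The plan refers only to basic clinical information, which it does not define. Many of the measurements overlap (SPPB contains gait speed and the chair-stand test), so independence fails.
- No correlation is given, and enrolment by score cut-offs may lower it. At r = 0.3 the gain over an unadjusted comparison is only 9%.
- Propensity matching may include baseline scores. The plan does not say so, and matching is not adjustment of the outcome.
- If allocation was really by community, as the parenthesis in 4.1 could suggest, baseline differences between individuals are not simply chance, and ordinary robust errors would ignore clustering. Baseline adjustment would still be wanted.
- A same-instrument baseline is uncertain for depression. Sections 3.2 and 5.1 use GDS-5, whereas 6.1 records GDS-15 or the Zung scale.

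What remains is that no stated analysis uses the outcome's own baseline efficiently, and that the only tests named are used where they are least informative.

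**Conclusion.** The point holds for the secondary scales. It does not touch the primary feasibility targets (recruitment, training, satisfaction). It concerns efficiency and clarity of estimation and is not evidence of bias.

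Over an assumed r of 0.3 to 0.8, the adjusted analysis has 0.65 to 0.90 of the variance of a change-score comparison, and 0.91 to 0.36 of the variance of an unadjusted month-6 comparison. The direction holds for any r between 0 and 1 under equal SDs and a common slope, but the size cannot be fixed from the protocol. The 34% figure for baseline tests assumes valid individual randomisation and 8 independent items.

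**What to change.** In section 4.2:

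1. Show baseline characteristics by arm descriptively, without P values.
2. For each secondary scale, in all randomised participants with a month-6 score, fit a linear model of the month-6 score on arm and the baseline score of the same instrument. Use heteroscedasticity-robust standard errors whatever the shape of the distribution. Report the adjusted mean difference with its 95% confidence interval.
3. State that this replaces the matched or change comparison for these scales.
4. Use one depression instrument at both baseline and month 6, after reconciling 3.2, 5.1 and 6.1.
5. State the unit of allocation. If it was the community, use cluster-robust standard errors.

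Section 6.3 should also confirm that the month-6 assessment in both arms includes all five scales, since its follow-up list names only ADL among them.

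The cost is protocol wording and a small amount of analysis work. No new data are needed where the same instrument is already recorded at both times; the depression scale is the one place where this has to be settled first.
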